Understanding the PK/PD relationship of colistin has been an area of considerable research in recent years [1, 50 – 57]. In fact, a recent clinical PK study in 105 critically ill patients developed the first evidence-based guidelines for dosing CMS to achieve a desired target steady state plasma concentration of formed colistin in patients with varying degrees of renal function [50]. In this large PK study, a population PK model was developed that indicated that creatinine clearance and body weight are significant covariates on the PK of CMS and colistin. Population PK based simulations were used to derive suggested loading and maintenance dosing regimens for patients of varying weight and renal function, including those on hemodialysis and continuous renal replacement, in order to obtain average target concentrations at steady state of 2.5 mg/L. This model serves as the basis of dosing instructions in this study (see [Table 12](#), Section 5.2.1.1), with minor adjustments made to the proposed schema including a constant (rather than weight-based) loading dose given to patients of varying weights and creatinine clearance. Specifically, simulations of a constant loading dose of 300 mg of CBA (~9 million IU or 720 mg CMS) for patients of varying weights and renal function indicate that the PK target is achieved more quickly and there is less variation among individuals in colistin PK. These simulations also indicate that as renal function increases, steady state is achieved more slowly following a loading dose. If maintenance dosing is initiated after 12 hours, rather than 24 hours, steady state is essentially achieved immediately following the loading dose. Based on these results, the published dosing scheme [50] has been modified to incorporate these changes (see [Table 12](#), Section 5.2.1.1). As both recommended in the published model-based recommendations [50] and the package circular, regardless of renal function, with the exception of the first 24 hours of therapy, subjects will not be administered more than the maximum total daily dose of 300 mg CBA (~ 9 million IU or 720 mg CMS). It is recognized that concerns for potential nephrotoxicity by colistin may limit the total daily amount of CMS that can be administered. However, data suggest that kidney damage is associated with total cumulative dose and the duration of CMS therapy [58]. Given that initial therapy is likely critical to rapid clearance of the infection and thus potentially shorter duration of therapy, an initial 24-hour period of exposure to doses exceeding the package circular recommendations will be beneficial to the success of therapy, and hence the efficacy of the treatment.

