5.2.1 Dose Selection/Modification

5.2.1.1 Dose Selection

For subjects with renal insufficiency, the dose of IMI/REL (in Treatment Group 1 or Treatment Group 3) and IMI (in Treatment Group 2) must be adjusted based upon the degree of renal function impairment, as determined by the estimated or actual creatinine clearance. It is important to note that if a change in the subject's creatinine clearance during IV study therapy could result in dosage adjustments at any time during IV therapy. Dose adjustments according to creatinine clearance are included in [Table 11](#).

Creatinine clearance in mL/min may be calculated from serum creatinine concentration by the C-G equation:

$$\text{Creatinine clearance (Males)} = \frac{(\text{weight in kg}) \times (140 - \text{minus age})}{(72) \times (\text{creatinine in mg/dL})}$$

$$\text{Creatinine clearance (Females)} = 0.85 \times \text{the value obtained using the formula above}$$

Subjects in Treatment Group 2 will also receive colistin as CMS. Upon randomization and initiation of IV study therapy, the dosage of the first dose of CMS for Treatment Group 2 subjects will depend on the subject's previous history of receipt of colistin within the 72 hours prior to entry in the study. Specifically, if a loading dose >200mg CBA (corresponding to ~ 470 mg CMS or 5.9 million IU) was administered prior to entry, the subject should begin maintenance doses described in [Table 12](#) upon initiation of IV study therapy. It should be noted that a loading dose is defined based on the dosage of any individual dose(s) administered rather than the total dosage over a series of doses in a subject who has received >1 dose prior to entry. If the subject has not received a loading dose (i.e., an individual dose \geq 200 mg CBA) prior to study entry, the protocol-specified loading dose of CMS of 300 mg CBA (corresponding to ~ 720 mg CMS or ~9 million IU) should be provided as shown in [Table 12](#), regardless of the dosage previously administered.

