Twelve (12) hours after the initial loading dose, maintenance dosing will begin and then continue every 12 hours (q12h) thereafter. The maintenance dose of CMS will be based on creatinine clearance according to [Table 12](#). Creatinine clearance may be calculated from serum creatinine concentration by the equation previously provided. It is important to note that a change in the subject's creatinine clearance during IV study therapy could result in dosage adjustments at any time during IV therapy.

Subjects assigned to Treatment Group 1 will receive a matching placebo for CMS on the same schedule as subjects in Treatment Group 2 (first dose upon initiation of therapy followed by q12h maintenance doses beginning 12 hours later). Since Treatment Group 3 is open-label, no placebo will be administered to subjects enrolled into this Treatment Group.

Table 11 Administration Dosage of IMI/REL and IMI According to Renal Function

Creatinine Clearance (mL/min)	IMI/REL^a	IMI
≥ 90	500/250 mg q6h	500 mg q6h
< 90 to ≥ 60	400/200 mg q6h	400 mg q6h
< 60 to ≥ 30	300/150 mg q6h	300 mg q6h
< 30 to ≥ 15	200/100 mg q6h	200 mg q6h
^a IMI/REL is provided as a single vial in a fixed-dose combination; therefore, the dose for each component will be adjusted equally during preparation. For example, a Treatment Group 1 subject who has a creatinine clearance of 50 mL/min should receive a 150 mg q6h dose of REL according to the table. Since the dose is reduced by 50% during preparation, the total mg of IMI would also be reduced by 50%, thus resulting in a 300 mg q6h dose of IMI.		

Table 12 Administration Dosage of Loading and Daily Maintenance Doses of CMS According to Renal Function

Creatinine Clearance (mL/min)	Loading Dose^a	Maintenance Dose^b
≥ 90	300 mg CBA (~720 mg CMS or ~9 million IU)	150 mg CBA (~360 mg CMS or ~4.5 million IU)
< 90 to ≥ 60		150 mg CBA (~360 mg CMS or ~4.5 million IU)
< 60 to ≥ 30		115 mg CBA (~270 mg CMS or ~3.4 million IU)
< 30 to ≥ 15		75 mg CBA (~180 mg CMS or ~2.3 million IU)
CMS = colistimethate sodium; CBA = colistin base activity.		
^a If a loading dose ≥ 200 mg CBA (~470 mg CMS or ~5.9 million IU) was administered prior to study entry, the subject should begin maintenance doses upon initiation of IV study therapy. If the subject has not previously received a loading dose, a loading dose should be provided as described, regardless of the dosage previously administered.		

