^b With the exceptions noted in footnote a, the maintenance dose will be administered 12 hours following administration of the loading dose and will be administered every 12 hours thereafter.		

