5.2.2 Timing of Dose Administration

The dosage of the IV study drugs may be adjusted based on the subject's renal function as shown in [Table 11](#) and [Table 12](#). The frequency of IMI/REL and of IMI administration will be every 6 hours (q6h). Each infusion should be administered within 60 minutes of the scheduled dose.

The frequency of CMS administration (or placebo for CMS) will be every 12 hours (q12h). A loading dose (300 mg CBA [corresponding to ~720 mg CMS or ~9 million IU]) will be administered upon initiation of study therapy, except in certain subjects who have been administered colistin prior to study entry (see Section 5.2.1.1). Twelve (12) hours following the loading dose, the maintenance dose will be initiated and then continued q12h thereafter.

Since IMI-containing therapy will be administered q6h and CMS (or placebo to CMS) will be administered q12h, CMS (or placebo to CMS) will be administered at the same hour of the day as the IMI-containing study therapy (IMI or IMI/REL) at each 12-hour interval. An illustration of the dosing scheme for each treatment group is provided in [Figure 2](#).

IMI/REL (Treatment Group 1 or Treatment Group 3), IMI (Treatment Group 2) and CMS (Treatment Group 2) should be administered over 30 ± 5 minutes. The study therapy must NOT be administered simultaneously through the same infusion line/lumen with any other drugs (including other IV study or IV non-study drugs). If another IV drug is required either prior to or after study drug and only 1 line/lumen is available, an appropriate volume of saline flush must be used between IV infusions. In instances when IMI/REL or IMI require administration at the same hour of the day as the CMS (or placebo to CMS), the 2 infusions should be administered either 1) sequentially with the IMI-containing infusion first followed by an appropriate volume of saline flush prior to administration of the CMS/placebo OR, 2) via a separate infusion line at the same time as the CMS/placebo.

Additional details for preparation and administration of study drug are provided in a separate Pharmacy Manual.

Hour	Treatment Group 1 /3 ^a		Treatment Group 2	
	IMI/REL ^b (q6h) + Placebo for CMS (q12h)		CMS ^c (q12h) + IMI ^b (q6h)	
0	IMI/REL	Placebo to CMS	CMS	IMI
2				
4				
6	IMI/REL			IMI
8				
10				
12	IMI/REL	Placebo to CMS	CMS	IMI
14				
16				
18	IMI/REL			IMI
20				
22				
24	IMI/REL	Placebo to CMS	CMS	IMI
26				
28				
30	IMI/REL			IMI
32				
34				

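### Table 12 footnote a starts CMS maintenance at hour 0 after a pre-entry dose of 200 mg CBA or more however recent, so at gaps under 12 hours doses come early (at CrCl ≥60, 500–600 mg CBA in the 24 hours after the load against 450 mg planned)

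*Combined protocol and SAP*

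**What the plan says.** For a subject without prior colistin, Table 12 gives a 300 mg CBA load at hour 0 and then maintenance every 12 hours: 150 mg at CrCl ≥60 mL/min, 115 mg at 30 to <60 and 75 mg at 15 to <30.

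For a subject already loaded, footnote a says that when a load of 200 mg CBA or more "was administered prior to study entry, the subject should begin maintenance doses upon initiation of IV study therapy". The matching text in 5.2.1.1 applies "if a loading dose >200mg CBA (corresponding to ~ 470 mg CMS or 5.9 million IU) was administered prior to entry". It writes a strict inequality where the table does not, which matters only for a dose of exactly 200 mg. Footnote b adds: "With the exceptions noted in footnote a, the maintenance dose will be administered 12 hours following administration of the loading dose". Section 5.2.2 repeats that the study load is given at the start "except in certain subjects who have been administered colistin prior to study entry".

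The only time references are the 72-hour look-back in 5.2.1.1 and exclusion 4 in 5.1.3.1. Exclusion 4 bars only subjects with more than 24 hours of systemic colistin in the 72 hours before study therapy. A single load given an hour before study start is therefore admissible.

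**The concern.** The rule tests how large the earlier dose was and never asks when it was given. Footnote b removes the 12-hour spacing for exactly these subjects, and the visible text puts nothing in its place. Someone loaded shortly before study start would get a maintenance dose almost on top of the load.

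The rationale does not describe that schedule. Section 4.2.2.2 supports a load followed by maintenance at 12 hours, brought forward from 24 hours in the published scheme: "If maintenance dosing is initiated after 12 hours, rather than 24 hours, steady state is essentially achieved immediately following the loading dose". It accepts a high first day on that basis. It also recognises that "concerns for potential nephrotoxicity by colistin may limit the total daily amount of CMS that can be administered".

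What is at stake is early colistin exposure in Group 2. The overdose definition in 7.2.1 would not flag it, because that definition refers to the Table 12 doses and the study doses given would comply with Table 12.

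**Working it through.** **Inputs.** Study load 300 mg CBA; maintenance M = 150, 115 or 75 mg (Table 12). Pre-entry load L: 200 mg is the footnote a threshold, and 300 mg is an assumed upper value equal to the study load, since the documents set no limit. t is the number of hours from L to study start, with t < 12. L is taken as the only pre-study colistin dose.

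**The plan's own figures.** Daily maintenance at CrCl ≥60 is 2 × 150 = 300 mg, as in Table 10. The planned first 24 hours hold 300 + 150 = 450 mg (doses at hours 0 and 12). This agrees with Table 10 footnote d, which says only that the first day exceeds 300 mg.

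**Current rule.** Counting from the load, doses fall at 0 (L), t (M) and t + 12 (M), and the next at t + 24. For any t < 12 the 24 hours after the load hold L + 2M. This exceeds 300 + M when L > 300 − M.

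| CrCl (mL/min) | Planned, 300 + M | Current, L + 2M | 12-hour wait, L + M | Current exceeds plan if L > |
|---|---|---|---|---|
| ≥60 | 450 | 500–600 | 350–450 | 150 |
| 30 to <60 | 415 | 430–530 | 315–415 | 185 |
| 15 to <30 | 375 | 350–450 | 275–375 | 225 |

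All entries are mg CBA. At CrCl ≥60 the excess is 50–150 mg, or 50/450 = 11% to 150/450 = 33%. In the lowest band the current rule is above plan only for loads over 225 mg.

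**Dependence on the gap.** The 24-hour total is the same for every t < 12, so it hides how much the gap matters. The shift is 12 − t hours. With L = 300 mg at CrCl ≥60, 600 mg is reached t + 12 hours after the load, against 24 hours on plan. The cumulative dose runs one maintenance dose ahead for (12 − t)/12 of each interval.

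| t (h) | Shift (h) | 600 mg reached at (h) | Share of time one dose ahead |
|---|---|---|---|
| 1 | 11 | 13 | 92% |
| 3 | 9 | 15 | 75% |
| 6 | 6 | 18 | 50% |
| 11 | 1 | 23 | 8% |

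From t = 11 the shift is no more than the tolerance in 5.2.2 ("Each infusion should be administered within 60 minutes of the scheduled dose"). At t = 1 the 13 hours after the load hold 500–600 mg. The plan gives 450 mg over its first 13 hours, so the comparison also holds over equal windows.

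**What does not change.** The course total is L + 10M at any t for ten maintenance doses. Study drug alone in the first 24 hours is 2M = 300, 230 or 150 mg.

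**The case against.** The strongest reply is that, for a 300 mg load, this is the planned amount given sooner. The plan itself reaches 600 mg once the hour-24 dose is counted. Section 4.2.2.2 answers its own renal worry by noting that "data suggest that kidney damage is associated with total cumulative dose and the duration of CMS therapy", and the course total is not altered. It also argues that a high first day helps efficacy. After a load below 300 mg, an hour-0 maintenance dose can act as a top-up. All of this stands and limits the point to early exposure.

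Three stronger readings are tempting but unsupported.

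- **A dosing limit is broken.** The 300 mg daily maximum excepts the first 24 hours, and footnote b excepts footnote a. The excess appears only when the pre-entry load is counted.
- **More kidney injury, or a distorted nephrotoxicity comparison.** Table 19 is sensitive to single events: with none on IMI/REL, going from 2 to 3 comparator events moves p from 0.106 to 0.032. But nothing in the documents shows that the shift would cause an event.
- **A 12-hour wait reproduces the simulations.** Those used a constant 300 mg load and do not cover a 200–299 mg load followed by a wait.

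The protocol has other safeguards: exclusion 13 (investigator's judgement of added risk), a start any time on the day of assignment, daily reporting of creatinine clearance, and stopping below 15 mL/min. They may catch individual cases, but none sets the spacing. The Pharmacy Manual is not among the documents and may contain a timing rule.

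The fix also leaves the larger short-gap case untouched. At a 1-hour gap, a 199 mg dose followed by the full study load gives 199 + 300 + 150 = 649 mg in 13 hours. The step at the 200 mg threshold is now 649 − 500 = 149 mg and would become 649 − 350 = 299 mg.

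**Conclusion.** The point holds as a gap in the dosing rule with a limited effect. A stated rule produces a dose spacing that the protocol's rationale nowhere describes. At CrCl ≥60 it puts 50–150 mg CBA more into the 24 hours after the load than the planned 450 mg. This is material when the gap is a few hours and negligible from about 11 hours.

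The size rests on the assumed 300 mg upper load, on a single pre-study dose, and on leaving the hour-24 dose out of the planned day. The 1-hour gap is an illustration; the documents do not say how often short gaps would occur. The case for acting is that keeping the protocol's own 12-hour interval costs little. It is a worthwhile improvement and does not rest on demonstrated harm.

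**What to change.** Reword Table 12 footnote a and the matching sentence in 5.2.1.1 along these lines:

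> After a single pre-entry colistin dose of 200 mg CBA or more, no study load is given. The first CMS maintenance dose (matching placebo in Treatment Group 1) follows 12 hours after the last pre-study colistin dose, or at hour 0 if 12 hours or more have passed, and then q12h. IMI/REL or IMI starts at hour 0 in all subjects.

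Carry the exception into the Group 1 placebo sentence of 5.2.1.1, the same-hour sentence of 5.2.2 and a footnote to Figure 2. If the Pharmacy Manual already has such a rule, move it into the protocol.

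The mMITT definition (8.1.1, Table 16 and 8.2.4.1) requires a dose of every drug in the assigned regimen. Add that a subject whose first CMS or placebo dose is deferred under this rule is not excluded for stopping or dying before it. Delaying placebo equally may not balance such losses, because Group 1 is on active IMI/REL meanwhile and the planned mMITT groups are only about 30 and 15.

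Costs:

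- The unblinded pharmacist needs one more clock time, that of the last pre-study colistin dose.
- Some CMS or placebo infusions fall off the IMI hours.
- After a 200 mg load the 24-hour total is 350 mg against 450 at CrCl ≥60 (−22%), 315 against 415 (−24%) and 275 against 375 (−27%) in the lower bands. The current rule already gives these totals at a 12-hour gap.

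The minimum of 10 or 14 CMS doses still fits. With the first dose at hour d < 12, the 10th falls at d + 108 < 120 hours and the 14th at d + 156 < 168 hours. No extra subjects or procedures are needed. A recent dose below 200 mg followed by the full study load needs its own rule.

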5.2.2 Timing of Dose Administration

The dosage of the IV study drugs may be adjusted based on the subject's renal function as shown in [Table 11](#) and [Table 12](#). The frequency of IMI/REL and of IMI administration will be every 6 hours (q6h). Each infusion should be administered within 60 minutes of the scheduled dose.

The frequency of CMS administration (or placebo for CMS) will be every 12 hours (q12h). A loading dose (300 mg CBA [corresponding to ~720 mg CMS or ~9 million IU]) will be administered upon initiation of study therapy, except in certain subjects who have been administered colistin prior to study entry (see Section 5.2.1.1). Twelve (12) hours following the loading dose, the maintenance dose will be initiated and then continued q12h thereafter.

Since IMI-containing therapy will be administered q6h and CMS (or placebo to CMS) will be administered q12h, CMS (or placebo to CMS) will be administered at the same hour of the day as the IMI-containing study therapy (IMI or IMI/REL) at each 12-hour interval. An illustration of the dosing scheme for each treatment group is provided in [Figure 2](#).

IMI/REL (Treatment Group 1 or Treatment Group 3), IMI (Treatment Group 2) and CMS (Treatment Group 2) should be administered over 30 ± 5 minutes. The study therapy must NOT be administered simultaneously through the same infusion line/lumen with any other drugs (including other IV study or IV non-study drugs). If another IV drug is required either prior to or after study drug and only 1 line/lumen is available, an appropriate volume of saline flush must be used between IV infusions. In instances when IMI/REL or IMI require administration at the same hour of the day as the CMS (or placebo to CMS), the 2 infusions should be administered either 1) sequentially with the IMI-containing infusion first followed by an appropriate volume of saline flush prior to administration of the CMS/placebo OR, 2) via a separate infusion line at the same time as the CMS/placebo.

Additional details for preparation and administration of study drug are provided in a separate Pharmacy Manual.

Hour	Treatment Group 1 /3 ^a		Treatment Group 2	
	IMI/REL ^b (q6h) + Placebo for CMS (q12h)		CMS ^c (q12h) + IMI ^b (q6h)	
0	IMI/REL	Placebo to CMS	CMS	IMI
2				
4				
6	IMI/REL			IMI
8				
10				
12	IMI/REL	Placebo to CMS	CMS	IMI
14				
16				
18	IMI/REL			IMI
20				
22				
24	IMI/REL	Placebo to CMS	CMS	IMI
26				
28				
30	IMI/REL			IMI
32				
34				
36	IMI/REL	Placebo to CMS	CMS	IMI
38				
40				
42	IMI/REL			IMI
44				
46				
48	IMI/REL	Placebo to CMS	CMS	IMI
IMI/REL = imipenem/cilastatin/relebactam; IMI = Imipenem/cilastatin; CMS = colistimethate sodium				
^a Subjects in Treatment Group 3 will receive IMI/REL only (no placebo) since therapy will be provided open-label.				
^b The dosage of IMI/REL or IMI may be adjusted based on renal sufficiency according to Table 11.				
^c The dosage of CMS may be adjusted based on renal sufficiency according to Table 12.				

Figure 2 Dosing Scheme for Study Therapies

5.2.3 Trial Blinding/Masking

Treatment Groups 1 and 2

A double-blind/masking technique will be used for randomized subjects (Treatment Group 1 and Treatment Group 2). IMI/REL, IMI, CMS, and placebo to CMS will be dispensed in a blinded fashion to these subjects. All study therapy supplies will be provided in an open-label fashion to the sites. Since randomized subjects (Treatment Group 1 and Treatment Group 2) will be provided study therapy in a blinded fashion, an Unblinded Study Pharmacist (or qualified designee) at the study site will be responsible for preparing all of the IV study therapy for this study; this individual(s) will not be involved in any safety or efficacy evaluations of the study participants. Due to a slight difference in the appearance of CMS solution for infusion and the placebo infusion, the infusion bags will be covered in an opaque sleeve by an Unblinded Study Pharmacist (or qualified designee) to ensure that other study personnel and all subjects remain blinded to clinical material assignment. The intravenous

line (through which the infusion is administered) does not require opaque covering as the differences between the clinical materials are not visually distinguishable within the tubing.

Once each infusion is properly prepared and masked with an opaque sleeve, the study therapy will be administered by qualified trial site personnel. The personnel involved in the administration of the study infusion treatment should be unaware of the treatment group assignments. Similarly, the subject, the investigator, and Sponsor personnel or delegate(s) who are involved in the clinical evaluation of the subject should also remain unaware of the treatment group assignments.

See Section 7.1.4.2, Blinding/Unblinding, for a description of the method of unblinding a subject during the trial, should such action be warranted.

Treatment Group 3

Subjects who are enrolled to receive IMI/REL in Treatment Group 3 will do so in an open-label fashion.

